## 5.7 Microbiologically Evaluable (ME) Analysis Sets

The ME Analysis Sets (ME-EOT, ME-TOC and ME-LFU) will consist of all subjects who meet criteria for inclusion in both the microITT and the CE-EOT (ME-EOT) Analysis Set, the CE-TOC (ME-TOC) Analysis Set or the CE-LFU (ME-LFU) Analysis Set. Subjects who have CABP caused *only* by a pathogen(s) resistant to moxifloxacin or lefamulin will be excluded from the ME Analysis Sets. Resistance is defined as: 1) a pathogen resistant to moxifloxacin or non-susceptible to lefamulin based on susceptibility results from the central laboratory, or 2) a pathogen in the *Enterobacteriaceae* family or a non-fermenting Gram-negative pathogen (with the exception of *Legionella pneumophila* and *Moraxella catarrhalis*), unless susceptibility data from the central laboratory is available and indicates the pathogen is susceptible to both moxifloxacin (Table 9) and lefamulin (Table 10).

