#### **4.0 PATHOGEN IDENTIFICATION**

All microbiology data will be reviewed by the Sponsor for pathogen identification. A pathogen is defined as bacteria implicated as causative in a subject's CABP and will be determined separately for each subject. Baseline pathogens and post-baseline pathogens will be identified.

Additional details regarding the pathogen review process and determination are included in the Evaluability Review Plan.

Baseline for microbiologic specimens is defined as the 24-hour period prior to the administration of the first dose of study drug and the 24 hours after the first dose of study drug. A pathogen identified from a respiratory (pleural fluid, bronchoalveolar lavage (BAL), sputum), blood for culture, urine, nasopharyngeal or oropharyngeal specimen collected at baseline is considered a baseline pathogen. An atypical pathogen identified by serology is considered a baseline pathogen if the baseline sample is collected in the 24-hour period prior to the administration of the first dose of study drug or the 24 hours after the first dose of study. A Gram stain from a specimen collected at baseline is considered a baseline Gram stain.

If more than 1 specimen is taken during the baseline period, all specimens will be reviewed for pathogen identification. If the same pathogen (based on genus and species) is identified from more than 1 specimen, the pathogen with the highest minimum inhibitory concentration (MIC) to study drug received will be considered the baseline pathogen. If the pathogens have the same MIC to study drug received, the one with the highest accession number will be considered the baseline pathogen.

Post-baseline is defined as the period starting 24 hours after the first dose of study drug. A pathogen identified from a specimen collected post-baseline is considered a post-baseline pathogen. Only pathogens identified by culture of the sputum, BAL, pleural fluid or blood are considered post-baseline pathogens.

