Baseline pathogens will be summarized by treatment group and overall, by genus and species, and diagnostic modality for the microITT, microITT-2, and ME-TOC Analysis Sets. The number and percentage of subjects with specimens tested, by testing modality, and the number and percentage of subjects with specimens positive for a pathogen and the specific pathogen (genus and species) will be presented. The number and percentage of subjects with monomicrobial or polymicrobial gram-positive or gram-negative pathogen infections, only atypical pathogens, a mixture of gram-positive and gram-negative pathogens, a mixture of gram-positive and atypical pathogens, a mixture of gram-negative and atypical pathogens or a mixture of gram-positive, gram-negative and atypical pathogens will be summarized by treatment group and overall for the microITT, microITT-2 and ME-TOC Analysis Sets.

The MIC distribution detailing the number and percentage of pathogens at the respective MIC values and the cumulative distribution will be presented for lefamulin and moxifloxacin by baseline pathogen, phenotype and study drug for both treatment groups combined and by treatment group for subjects in the microITT and ME-TOC Analysis Sets. Disk diffusion zone diameters for lefamulin and moxifloxacin will be summarized by baseline pathogen, phenotype, and study drug for both treatment groups combined and by treatment group for subjects in the microITT and ME-TOC Analysis Sets. Scatter plots of the MIC to lefamulin versus the disk diffusion zone diameter will be provided for *Streptococcus pneumoniae*, *Haemophilus influenzae*, *Staphylococcus aureus*, and *Moraxella catarrhalis*, as long as there are at least 10 pathogens in the lefamulin group.

The minimum inhibitory concentration 50 (MIC50), 90 (MIC90), and range of lefamulin and moxifloxacin for baseline pathogens and susceptibility (susceptible and resistant, based on MIC and zone diameter) of pathogens to lefamulin and moxifloxacin will be summarized by baseline pathogen for both treatment groups combined and by treatment group for subjects in the microITT and ME-TOC Analysis Sets. MIC50 and MIC90 will be provided only where there are at least 10 pathogens of a particular species; range will be provided for all pathogens.

Baseline pathogens are considered susceptible (S), intermediate (I), or resistant (R) to moxifloxacin and S or non-susceptible (NS) to lefamulin according to the criteria in [Table 9](#) and [Table 10](#).

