**Table 9. Interpretive Criteria for Moxifloxacin for CABP Pathogens According to CLSI Guidelines**

Pathogen	Moxifloxacin MIC breakpoint a [µg/mL]			Moxifloxacin Disk Diffusion Zone Diameter a [mm]		
	S	I	R	S	I	R
Streptococcus pneumoniae	≤ 1	2	≥ 4	≥ 18	15-17	≤ 14
Staphylococcus spp.	≤ 0.5	1	≥ 2	≥ 24	21-23	≤ 20
Haemophilus influenzae	≤ 1	-	-	≥ 18	-	-
Moraxella catarrhalis	-	-	-	-	-	-
Legionella pneumophila	-	-	-	-	-	-
Mycoplasma pneumoniae b	≤ 0.25	-	≥ 0.5	-	-	-

S=susceptible, I=intermediate, R=resistant

a According to [CLSI M100-S25 \(2015\)](#)

b Breakpoints according to [CLSI M43-A \(2011\)](#)

**Table 10. Proposed Tentative Susceptibility Interpretive Criteria for Lefamulin for CABP Pathogens Based on *In Vitro* Data Determined According to CLSI Guidelines**

Pathogen	Lefamulin MIC breakpoint a [µg/mL]		Lefamulin Disk Diffusion Zone Diameter a [mm]	
	S	NS	S	NS
Streptococcus pneumoniae	≤ 1	> 1	≥ 19	< 19
Staphylococcus spp.	≤ 1	> 1	≥ 20	< 20
Haemophilus influenzae	≤ 2	> 2	≥ 20	< 20
Moraxella catarrhalis	≤ 1	> 1	≥ 20	< 20
Legionella pneumophila	≤ 1	> 1	- b	- b
Mycoplasma pneumoniae	≤ 1	> 1	- b	- b

S=susceptible, NS=non-susceptible

a The current absence of data on resistant isolates except for *S. aureus* precludes defining any category other than “susceptible.”

b No disk diffusion zone diameter criteria have been established for *M. pneumoniae* and *L. pneumophila*.

By-subject listings of pathogen MICs, susceptibilities, and disk diffusion zone diameters will also be provided.

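### SAP 5.7 screens the ME sets more strictly for lefamulin susceptibility than for moxifloxacin susceptibility, which can tilt the secondary and additional ME analyses toward lefamulin by an unknown, probably small amount

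*SAP*

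**What the plan says.** SAP 5.7 builds the ME sets from microITT and the matching CE set, then adds a resistance exclusion: "Subjects who have CABP caused *only* by a pathogen(s) resistant to moxifloxacin or lefamulin will be excluded from the ME Analysis Sets". The definition has two limbs.

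- Limb 1: "Resistance is defined as: 1) a pathogen resistant to moxifloxacin or non-susceptible to lefamulin based on susceptibility results from the central laboratory".
- Limb 2 counts Enterobacteriaceae and non-fermenting Gram-negatives (other than L. pneumophila and M. catarrhalis) as resistant, "unless susceptibility data from the central laboratory is available and indicates the pathogen is susceptible to both moxifloxacin (Table 9) and lefamulin (Table 10)".

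SAP 8.3 sets the categories: "Baseline pathogens are considered susceptible (S), intermediate (I), or resistant (R) to moxifloxacin and S or non-susceptible (NS) to lefamulin". The breakpoints are in SAP Table 9 (moxifloxacin) and Table 10 (lefamulin).

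For repeat isolates of one species, SAP 4.0 says that "the pathogen with the highest minimum inhibitory concentration (MIC) to study drug received will be considered the baseline pathogen".

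Protocol 9.3.6 defines the ME sets as microITT plus CE, with no resistance exclusion. SAP 9.0 does not list the exclusion as a change.

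**The concern.** An evaluable-population rule in an active-controlled trial should ask the same question of both drugs. Here a pathogen must reach the top moxifloxacin category to count as resistant, but need only miss the susceptible category for lefamulin. The ME population is therefore cleared of subjects whose only pathogens tested as not lefamulin-susceptible. It keeps subjects whose only pathogens are not moxifloxacin-susceptible, provided they fall short of category R or have no R category.

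If the retained subjects do worse on moxifloxacin, the ME difference moves toward lefamulin. At stake are the ME-TOC secondary analyses (IACR in SAP 8.5.3.3, by-pathogen response in SAP 8.5.3.4) and the additional ME analyses in SAP 8.5.4.

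The isolate choice in SAP 4.0 raises a second issue: ME membership may depend on the assigned drug even when the microbiology is identical.

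**Working it through.** The plan gives no figure on this point, so there is none to reproduce. The check sets the rule against the two breakpoint tables, then bounds the size.

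**1. What limb 1 does, by species (MIC in µg/mL)**

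| Species | Moxifloxacin, Table 9 | Lefamulin, Table 10 | Not moxifloxacin-susceptible but kept |
|---|---|---|---|
| S. pneumoniae | S ≤1, I 2, R ≥4 | S ≤1, NS >1 | MIC 2 |
| Staphylococcus spp. | S ≤0.5, I 1, R ≥2 | S ≤1, NS >1 | MIC 1 |
| H. influenzae | S ≤1, no I or R | S ≤2, NS >2 | any MIC >1 |
| M. catarrhalis | no criteria | S ≤1, NS >1 | cannot be classified |
| L. pneumophila | no criteria | S ≤1, NS >1 | cannot be classified |
| M. pneumoniae | S ≤0.25, R ≥0.5 | S ≤1, NS >1 | none |

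For three of the six listed organisms the moxifloxacin half of limb 1 can never act, while the lefamulin half can. For H. influenzae this need not be an empty case. Protocol 1.3 gives a lefamulin MIC90 of 2, exactly the susceptible limit, so up to 10% of those isolates could lie above it.

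**2. Does the rule differ by arm?** Not as written in SAP 5.7. Subjects with only lefamulin-NS or only moxifloxacin-R pathogens leave both arms, and moxifloxacin-intermediate subjects stay in both. What changes is the susceptibility mix of the set.

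**3. Isolate choice under SAP 4.0.** Take one subject with two S. pneumoniae isolates and no other pathogen. Isolate A has lefamulin MIC >1 and moxifloxacin MIC ≤1. Isolate B has lefamulin MIC ≤1 and moxifloxacin MIC 2.

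- On lefamulin, A is the baseline pathogen. It is NS, so the subject leaves.
- On moxifloxacin, B is the baseline pathogen. It is intermediate and lefamulin-susceptible, so the subject stays.

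The mirror case, with a moxifloxacin-R isolate, would remove a moxifloxacin subject and keep a lefamulin one. It takes two same-species isolates that differ in category, so it should be rare.

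**4. Size.** Let f be the share of moxifloxacin ME subjects kept only because of the looser bar, p the success rate of the other moxifloxacin ME subjects, and d the drop in success of the retained ones. Then

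observed moxifloxacin rate = (1 − f)p + f(p − d) = p − f·d,

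and the shift toward lefamulin is f·d, provided the same kind of subject does no worse than others on lefamulin.

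Neither f nor d is in the documents. The nearest figure is 1.0–1.1% levofloxacin resistance in S. pneumoniae (Protocol 1.3): one species, another drug, and resistance rather than intermediacy. The d = 85 column means that every retained subject fails, with p set to the 85% CE-TOC planning rate.

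| f (assumed) | d = 0 | d = 20 points | d = 40 points | d = 85 points |
|---|---|---|---|---|
| 0.5% | 0 | 0.1 | 0.2 | 0.4 |
| 1.1% | 0 | 0.2 | 0.4 | 0.9 |
| 2% | 0 | 0.4 | 0.8 | 1.7 |
| 5% | 0 | 1.0 | 2.0 | 4.3 |
| 10% | 0 | 2.0 | 4.0 | 8.5 |

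For example, 1.1% × 85 = 0.94 points, and 5% × 40 = 2.0 points.

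The table does not cover lefamulin-NS M. catarrhalis or L. pneumophila leaving the sets with no moxifloxacin counterpart. Protocol 1.3 gives lefamulin MIC90 values of 0.25 and 0.5 for these species, both below the cut of 1, so at most 10% of such isolates could lie above it.

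**The case against.** The strongest defence has four parts.

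- **The rule is arm-neutral and narrow.** This stands for SAP 5.7 taken alone. A subject leaves only if every causative pathogen qualifies, and limb 1 needs a central-laboratory result. A reader might infer that the ME sets drop every lefamulin-non-susceptible pathogen. The text does not support that: such a pathogen can remain in a mixed infection, pathogens found only by PCR, serology or urine antigen have no tested isolate, and C. pneumoniae is in neither table.
- **The categories differ because the data differ.** The first footnote to Table 10 says that missing data on resistant isolates (S. aureus excepted) rule out any category beyond susceptible. That explains using NS for lefamulin. It does not explain the looser bar for moxifloxacin, where not-susceptible is definable wherever Table 9 gives an S value. Keeping intermediate apart from resistant is a defensible convention alone, but not when the other drug is held to S or NS and limb 2 asks for susceptibility to both.
- **The information appears elsewhere.** This stands in part. SAP 8.5.3.3 and 8.5.3.4 report microITT, which has no resistance exclusion, beside ME-TOC. SAP 8.5.4 tabulates outcomes by MIC and zone diameter, and SAP 8.1 tabulates reasons for exclusion. None of these gives the ME comparison under a parallel rule.
- **Little depends on it.** This stands. The FDA primary analysis uses ITT and the EMA primary uses mITT and CE-TOC. ME-TOC IACR has a confidence interval but no stated margin, and by-pathogen response is only tabulated.

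The SAP 4.0 selection is also even-handed in form, since it pushes each arm toward exclusion for its own drug. It still lets identical isolates give different membership, which an evaluability rule should avoid.

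**Conclusion.** The unequal bar is plain from SAP 5.7 read with Tables 9 and 10. Any resulting bias from it would favour the test drug, and it reaches only the secondary and additional ME analyses.

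A reader might go further and conclude that the ME comparison is tilted. The documents do not show that. A tilt requires that subjects with only moxifloxacin-intermediate or above-breakpoint pathogens occur in the ME sets and do worse on moxifloxacin, and no figure is given for either.

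If 1.1% of moxifloxacin ME subjects are affected, the shift is 0 to about 0.9 points. It reaches 2 points only at about 5% with a 40-point drop. These figures rest on assumed f and d, and on such subjects doing no worse than others on lefamulin. The arm-dependent membership from SAP 4.0 is a separate defect, expected to be rare and not quantified. This is an inexpensive improvement, not a threat to the trial's main conclusions.

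**What to change.** In SAP 5.7 and 4.0:

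1. In limb 1, use non-susceptible for both drugs. For moxifloxacin this means I or R, or above the S breakpoint where Table 9 has no I or R category.
2. For species with criteria for only one drug (M. catarrhalis, L. pneumophila), do not apply the limb 1 exclusion. Step 1 alone would leave these two unequal.
3. Judge all baseline isolates of a pathogen against both drugs, in the same way in both arms. Keep the isolate chosen by MIC to the drug received only for the by-MIC and zone-diameter tables.
4. Add an ME-TOC sensitivity analysis without the resistance exclusion, which is the protocol 9.3.6 definition. Listing the exclusion in SAP 9.0 at the same time would record the departure from the protocol.

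The cost is SAP wording, minor reprogramming and slightly different ME set sizes. No new data are needed.

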## 5.8 Expanded Microbiological ITT (emicroITT) Analysis Set

The emicroITT Analysis Set will consist of all subjects in the ITT Analysis Set who have at least 1 baseline bacterial pathogen known to cause CABP as defined in Sections 4.1 and 4.2, except a

baseline pathogen from a sputum culture is defined using the presence of a Gram stain with  $\geq 10$  PMNs/LPF and  $< 10$  SECs/LPF rather than  $> 25$  PMNs/LPF and  $< 10$  SECs/LPF.

## **5.9 Pharmacokinetic (PK) Analysis Set**

The PK Analysis Set will consist of all subjects in the mITT Analysis Set who have concentration results from at least one pharmacokinetic sample.

## 6.0 DEFINITIONS OF OUTCOME MEASURES

Efficacy will be assessed, either programmatically or by the Investigator (as outlined below), at the following time points:

- 96 ± 24 hours (as described in Section 6.1) after the first dose of study drug (ECR only).
- EOT – within 2 days after the last dose of study drug.
- TOC – 5 to 10 days after last dose of study drug.
- LFU – Day 30 (±3 days) .

For the EOT, TOC and LFU assessments, subjects will be assigned an IACR (success, failure, or indeterminate at EOT and TOC, sustained success, relapse, prior failure or indeterminate at LFU). Early Clinical Response will be determined programmatically based on recorded symptom assessments that compare the assessments at Baseline and at 96 ± 24 hours after the first dose of study drug as defined in Section 6.1. The Investigator will not make a determination of Early Clinical Response and will make treatment decisions based on the subject's overall response to therapy. Microbiologic responses will be determined at EOT, TOC and LFU.

### 6.1 Primary Efficacy Outcome: Early Clinical Response

The primary efficacy outcome is the percentage of subjects with an ECR of responder at 96 ± 24 hours after the first dose of study drug in the ITT Analysis Set. Symptom definitions for the assessment are shown in [Table 2](#). Subjects will be programmatically defined as a **responder** if the following 4 criteria are met:

- Alive;
- Improvement in at least 2 of the 3 or 4 cardinal symptoms of CABP the subject presented with at baseline. Improvement is defined as a decrease by at least 1 level of severity;
- No worsening of any of the 4 cardinal symptoms of CABP. Worsening is defined as an increase by at least 1 level of severity for any symptom;
- Did not receive a concomitant antibiotic for the treatment of CABP up through the assessment of the cardinal symptoms of CABP.

**Table 2. Symptom Assessment for Early Clinical Response Assessment**

Symptom	Absent (0)	Mild (1)	Moderate (2)	Severe (3)
Dyspnea	Resolution (to pre-CABP baseline) or absence of dyspnea	Dyspnea on exertion (eg, climbing stairs)	Dyspnea with normal/routine activities (eg, walking)	Dyspnea at rest or requiring oxygen therapy
Cough	Resolution (to pre-CABP baseline) or absence of cough	Transient, does not interfere with normal activity	Frequent, interferes with normal activity or sleep	Constant, interferes with most or all activity or sleep
Production of purulent sputum	Resolution (to pre-CABP baseline) or absence of sputum production	Sputum production rarely causes difficulty or distress	Sputum production often causes difficulty or distress	Constant difficulty with sputum production
Chest pain	Resolution or absence of chest pain related to CABP	Transient, does not interfere with normal activity	Frequent, interferes with normal activity or sleep	Constant, interferes with most or all activity or sleep

Subjects will be programmatically defined as a **non-responder** if any of the following are met:

- Did not show an improvement in at least 2 of the 3 or 4 cardinal symptoms of CABP the subject presented with at baseline. Improvement is defined as a decrease by at least 1 level of severity; or
- Worsening of any of the 4 cardinal symptoms of CABP. Worsening is defined as an increase by at least 1 level of severity for any symptom; or
- Received a concomitant antibiotic for the treatment of CABP up through the assessment of the cardinal symptoms of CABP, or if no assessment was completed, up to 120 hours after the first dose of study drug (or randomization if the subject did not receive study drug); or
- Died from any cause up through the assessment of the cardinal symptoms of CABP, or if no assessment was completed, up through Study Day 5.

If more than 1 assessment of symptoms is obtained in the 96 ± 24 hour window, the following rules apply:

- Use the latest assessment of symptoms conducted in person occurring in the 96 ± 24 hour window
- If no assessment was conducted in person, use the latest assessment of symptoms conducted via a telephone call occurring in the 96 ± 24 hour window

If no assessment of symptoms (either in person or by telephone) was conducted in the 96 ± 24 hour window, the following rules apply:

- Use the latest assessment of symptoms conducted in person occurring 60 to <72 hours after the first dose of study drug
- If no assessment was conducted in person in the 60 to <72 hour window, use the latest assessment of symptoms conducted via a telephone call occurring 60 to <72 hours after the first dose of study drug

Subjects with missing data such that a response cannot be determined will be considered an indeterminate response. Subjects who are randomized and not treated or did not have at least 2 symptoms of CABP at baseline will also be considered to have an indeterminate response. Since the analysis of the primary outcome is based on the ITT Analysis Set, subjects with an indeterminate response are essentially considered non-responders. For the ITT Analysis Set, the percentage of ITT subjects considered responders for ECR is defined using the following formula (where the denominator is comprised of the total number of subjects in the ITT Analysis Set):

$$\frac{\text{Number of subjects who are a responder}}{(\text{Number of subjects who are a responder} + \text{Number of subjects who are a non-responder} + \text{Number of indeterminate subjects})} \times 100\%$$

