#### 9.8 Handling of Missing Data

For the primary outcome measure (FDA), if any data field needed to determine ECR is missing, the subject will be assigned a response of Indeterminate. Imputations for the missing times will be provided in the SAP. For analyses of the primary outcome, subjects with an indeterminate response are included in the denominator, and thus are considered Non-responders. A sensitivity analysis of the primary outcome will be conducted in which subjects with an indeterminate response are considered Responders.

For the outcome measure of IACR at EOT, TOC and LFU, missing data are considered as a response of Indeterminate. For analysis in the ITT, mITT and microITT Analysis Sets, indeterminate outcomes are included in the denominator and are thus, considered clinical Failures. By definition, subjects with an IACR of Indeterminate are excluded from the CE-EOT, CE-TOC, CE-LFU, ME-EOT, ME-TOC, and ME-LFU Analysis Sets.

A missing microbiological response is considered a presumed response based on the IACR. For analysis in the microITT Analysis Set, indeterminate outcomes are included in the denominator and are thus, considered microbiological failures. By definition, subjects with an IACR of Indeterminate are excluded from the ME Analysis Sets.

Handling of missing data for other efficacy and safety outcomes will be presented in the SAP.

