## 7.6 Handling of Missing Data

For ECR, missing data will be handled as follows:

- If any component of ECR is missing in the time frame detailed in Section 6.1 (unless the subject dies or is deemed a failure prior to this time point), or if the subject does not have at least 2 symptoms of CABP at baseline, ECR will be defined as an indeterminate.
- If the time of a post-baseline assessment of CABP symptoms obtained in the window for determination of ECR is missing but the date of the ECR assessment is known, the time will be imputed to noon on the date of the CABP symptom assessment. If the time of assessment of CABP symptoms obtained on or prior to the date of the first dose of study drug is missing, the time will be imputed to 00:00.
- Missing start and stop times of antibiotics will be set to 00:00 on the start and stop date of the antibiotic.
- For the analysis of ECR in the ITT Analysis Set, where ECR may be missing (indeterminate), all subjects in the ITT Analysis Set will be included in the denominator. Thus, subjects with an indeterminate response are essentially considered as a failure.

For IACR, missing data will be handled as follows:

- A missing IACR at the EOT Visit will be considered indeterminate at the EOT Visit.
- A missing IACR at the TOC Visit will be considered indeterminate unless the IACR at the EOT Visit is failure. An IACR of failure at the EOT Visit will be carried forward to the TOC Visit.
- A missing IACR at the LFU Visit will be considered indeterminate unless the IACR at the TOC Visit is failure. An IACR of failure at the TOC Visit will be carried forward to the LFU Visit.
- For the analysis of IACR at the EOT, TOC and LFU Visits in the mITT, microITT, microITT-2 and emicroITT Analysis Sets, where Clinical Response may be missing (indeterminate), all subjects who meet the analysis set criteria will be included in the denominator.
- For the analysis of IACR at the EOT, TOC and LFU Visits in the CE and ME Analysis Sets, subjects with a missing (indeterminate) IACR will not be included in the analyses, since by definition, subjects in the CE or ME Analysis Sets cannot have a missing IACR.

For microbiological response, missing data will be handled as follows:

- If a followup specimen for culture was not obtained, microbiological response at the EOT Visit will be determined based on the IACR at the EOT Visit.

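### The primary ECR rule picks the latest in-person record in the 72–120 h window with no completeness condition, so a blank symptom can make a subject a non-responder although another in-window record is complete and shows response

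*SAP*

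**What the plan says.** SAP 6.1 (the rules after Table 2) chooses one record by mode and recency:

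- First choice: "Use the latest assessment of symptoms conducted in person occurring in the 96 ± 24 hour window".
- Telephone data in the window: "If no assessment was conducted in person, use the latest assessment of symptoms conducted via a telephone call".
- Records from 60 to <72 h: "If no assessment of symptoms (either in person or by telephone) was conducted in the 96 ± 24 hour window, the following rules apply".

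Each fallback depends on whether an assessment was conducted. None depends on whether it was complete.

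A responder must also satisfy "No worsening of any of the 4 cardinal symptoms of CABP", so in general all four symptoms are needed.

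Three passages deal with missing items:

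- SAP 6.1: "Subjects with missing data such that a response cannot be determined will be considered an indeterminate response".
- SAP 7.6 assigns indeterminate under the condition "If any component of ECR is missing in the time frame detailed in Section 6.1", except after death or earlier failure.
- Protocol 9.8: "if any data field needed to determine ECR is missing, the subject will be assigned a response of Indeterminate".

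For the primary analysis, SAP 6.1 states that "subjects with an indeterminate response are essentially considered non-responders".

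**The concern.** More than one assessment can fall in the 48-hour window. Under Protocol 6.11 and Table 1, inpatients are assessed in person every day, and outpatients have daily telephone contact plus a required site visit. The selection rule can therefore land on an incomplete record while a complete one exists in the same window.

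This is the derivation of the FDA primary endpoint. Turning observed in-window responses into non-responses lowers the rate in both arms and costs some power. An equal proportional loss in both arms also shrinks a true deficit, which in a non-inferiority test raises the chance of a false conclusion.

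The wording leaves room for two programs to give different answers. SAP 6.1 reserves indeterminate for responses that cannot be determined, whereas SAP 7.6 refers to any component. The reasons for indeterminate listed in SAP 8.5.1 are no assessment and fewer than two baseline symptoms, so an incomplete assessment has no category.

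**Working it through.** **Tracing the rule.** Take an inpatient with complete in-person records at 78 h and 102 h, both showing two symptoms improved, none worse and no antibiotic. At 118 h chest pain is left blank.

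1. SAP 6.1 selects the 118 h record as the latest in-person one.
2. The telephone step does not apply, because an in-person assessment was conducted. The 60 to <72 h step does not apply, because the window is not empty.
3. Absence of worsening in chest pain cannot be shown. Under SAP 7.6 and Protocol 9.8 the subject is indeterminate and counts as a non-responder.

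An outpatient with an incomplete site visit and a complete in-window telephone record ends the same way.

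**Reproducing the plan's power.** Inputs from SAP 7.1: 79% in both arms, margin 10 points, one-sided alpha 0.025, continuity-corrected Z-test with unpooled variance, 369 per arm.

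- Uncorrected n = 2(0.79)(0.21)(1.960 + 1.282)²/0.10² = 348.6.
- Corrected n = (348.6/4)[1 + √(1 + 4/(348.6 × 0.10))]² = 368.4, so 369 per arm and 738 in total.
- SE = √(2 × 0.79 × 0.21/369) = 0.02999. Power = Φ((0.10 − 1/369)/0.02999 − 1.960) = Φ(1.285) = 90.05%.

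The plan's 90% is reproduced.

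**Size of the effect.** The documents give no rate of missing items, so one is assumed. If each of four items is missing independently with probability q, the share of incomplete assessments is x = 1 − (1 − q)⁴. As an upper bound, suppose every affected subject has another complete in-window record. The observed rate in each arm is then 0.79(1 − x), and power follows from the formula above.

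For type I error, take true rates of 79% and 69%, exactly at the margin. The same loss in both arms reduces the difference to −10(1 − x) points, and the chance of declaring non-inferiority is Φ((0.10 − 0.10(1 − x) − 1/369)/SE − 1.960), with SE taken at the reduced rates.

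| q (assumed) | x | ECR rate | Responders lost per arm | Power | Type I error |
|---|---|---|---|---|---|
| 0 | 0 | 79.0% | 0 | 90.05% | 2.05% |
| 0.25% | 1.0% | 78.2% | 2.9 | 89.3% | 2.21% |
| 0.5% | 2.0% | 77.4% | 5.8 | 88.5% | 2.37% |
| 1% | 3.9% | 75.9% | 11.5 | 87.1% | 2.72% |

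Type I error starts below 2.5% because of the continuity correction. It passes 2.5% only in the last row.

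**The existing sensitivity analysis.** The third analysis in SAP 8.5.2 sets every indeterminate to responder. With 2.0% incomplete, the primary rate is 77.4% and the sensitivity rate is 77.4% + 2.0% = 79.4%, against a target of 79%. The two bracket the target, but neither uses the complete record that was collected.

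**The case against.** The strongest reply is that this is an inference from silence. The SAP nowhere says that incomplete records are to be selected. The time-frame wording in SAP 7.6 could mean missing throughout the window, and the list of reasons in SAP 8.5.1 suggests that partial records were not considered. This stands as a limit on certainty. It does not remove the problem, because SAP 6.1 has no step that moves from an incomplete record to another one or combines records.

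A reader might infer that known responders are being recoded. The documents do not support that. In the example, chest pain at 118 h is unknown and may have worsened since 102 h. Protocol 6.1.1 makes the face-to-face visit the ECR assessment for outpatients, so an earlier or telephone response is a different observation. A conservative rule would be defensible if it were stated expressly.

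Nor does every blank item block a determination under SAP 6.1 alone. A symptom that was severe at baseline cannot rise a further level. The any-component wording of SAP 7.6 still gives indeterminate there, so the two sections need reconciling.

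The remaining points concern size, and they stand. Protocol 15.1 and 15.5 require missing data to be queried and accounted for, which should fill some blanks. At a fixed q, clustering of missing items gives fewer incomplete assessments than independence. The third sensitivity analysis would count the example subject as a responder, and the by-visit ECR summary in SAP 8.5.4.1 uses visits with non-missing baseline symptoms.

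**Conclusion.** The point holds as a gap in the primary-endpoint rule. Read together, SAP 6.1, SAP 7.6 and Protocol 9.8 can set aside a complete in-window assessment that shows response and count the subject as a non-responder.

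The effect is probably small. Under the assumed rates, and as an upper bound, power falls by about 0.8, 1.5 or 2.9 points, and type I error rises by about 0.2, 0.3 or 0.7 points. These figures assume independent item missingness, equal loss in both arms and another complete record for every affected subject.

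A reader might go further and infer a material bias between arms. A 2% loss of responders confined to lefamulin would cut power to 76.5%; confined to moxifloxacin, it would raise the chance of declaring non-inferiority to 96.1%. The documents give no reason to expect such an imbalance in a double-blind, double-dummy trial, so these figures show sensitivity only. The change is a cheap improvement; the primary analysis is not invalid without it.

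**What to change.** Amend the selection rule in SAP 6.1 before unblinding:

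1. Use the latest in-person assessment in the 72–120 h window from which ECR can be determined. If there is none, use the latest such telephone assessment in the window, then apply the 60 to <72 h steps in the same way.
2. If the latest in-person record is incomplete but already establishes non-response, it stands. This covers any recorded worsening and any record in which improvement in at least two baseline symptoms is no longer possible. Retaining recorded worsening alone would not be enough: with three symptoms back at baseline level and the fourth blank, two improvements are impossible, and an earlier record must not override that.
3. Keep the antibiotic and death cut-off tied to the latest assessment conducted, so that selecting an earlier record cannot hide a later failure.
4. Assign indeterminate only when no assessment in these windows allows a determination. Align SAP 7.6 with this, and add incomplete assessment to the reasons in SAP 8.5.1.

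The existing sensitivity analyses can stay as they are. The cost is a few sentences and a small change to the ECR program. The downside is that a few subjects will be classified on an earlier or telephone assessment while their status at the latest visit is partly unknown.
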